9.7.1.4 Reporting Adverse Events and Serious Adverse Events

At each visit, patients are to be queried regarding any AEs or SAEs that have occurred since the previous visit. Patients will be asked to volunteer information with a nonleading question such as, "How do you feel since your last visit?" Study site personnel will record all pertinent information in the patient's eCRF.

All AEs must be recorded on the appropriate AE reporting page of the patient's eCRF whether or not they are considered causally related to the study treatment.

For every AE, the investigator must:

- Provide an assessment of the seriousness of the event (ie, is it an SAE?), as well as the severity and causal relationship
- Document all actions taken with regard to the study treatment
- Detail any other treatment measures taken for the AE
- Document the outcome of the AE

In addition, patients are to be reminded, as described in the ICF and in accordance with Section 9.7.1, to notify site personnel of any AEs occurring during the 30 day post-study period. Any AEs reported by the patient (or patient representative) during this period are to be recorded in original source documents. AEs are also to be recorded in the eCRF if at least one of the following conditions is met: 1) the event meets the criteria for an SAE (see Sections 9.7.1.3 and 9.7.1.5), and/or 2) the event is judged by the Investigator to be potentially causally related to study treatment.

Any AEs that are ongoing at the time of the final protocol-defined study visit will be followed until the condition returns to prestudy status, has resolved or stabilized, or can be explained as being unrelated to the study treatment. If a follow-up visit is deemed necessary for appropriate safety surveillance, it will take place within 30 days of the final protocol-defined study visit.

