5.1.1.4.2 Adverse Events

Adverse event summaries will be presented for each safety population as follows:

- Post-Amendment 3 open-label safety population: by oxybutynin chloride gel dose level and overall
- Pre-Amendment 3 double-blind safety population: by treatment group, treatment and dose level, and overall
- Pre-Amendment 3 open-label safety population: by oxybutynin chloride gel dose level and overall
- Combined open-label safety population: by oxybutynin chloride gel dose level and overall

Adverse event summaries will be done overall and also for each age, weight, and sex group.

The following adverse event (AE) terms are defined:

An AE will be considered as a treatment-emergent adverse event (TEAE) if the AE initially occurs or increases in intensity on or after the first dose of study drug in the study. An event that occurs more than 30 days after the last dose of study drug will not be considered as treatment-emergent.

Table 5-15 AE Terms

Term	Description
Treatment- emergent	Double-blind period:
emergene	 First dose date of double-blind period ≤ event start date ≤ last dose date of double-blind period + 30 days if participant does not enter the 8-week open-label period; or First dose date of double-blind period ≤ event start date < first dose date of open-label period if participant enters the 8-week open-label period
	 Open-label period: First start date of open-label period ≤ event start date ≤ last dose date of open-label period + 30 days

AEs, encompassing abnormalities and surgeries reported as occurring after the Screening Visit, will be coded using MedDRA Version 19.1 or later. Unique participants reporting AEs in the following AE categories will be summarized for the groups defined above for each safety population as follows:

[figure not shown]

Table 5-16 AE Summaries

Parameter	Description	Timing	Methodology
Overall summary	Overall summary only for the following category: • Treatment-emergent AEs (TEAEs)	Study Period within Study Part ^{2,3} ; Combined open-label period	Categorical descriptives
TEAE	Overall summary and by SOC and PT	Study Period within Study Part ^{2,3} ; Combined open-label period	Categorical descriptives
TEAEs by severity	Overall summary and by SOC, PT, and intensity • Participants categorized overall and within each SOC and PT for the most intense occurrence	Study Period within Study Part ^{2,3} ; Combined open-label period	Categorical descriptives

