5.1.1.4.3 Clinical Laboratory Assessments

Clinical laboratory assessments will be summarized by treatment group, double-blind treatment/oxybutynin chloride gel sequence, or oxybutynin chloride gel only group, as applicable, and by analyte and visit for each safety population. Study Part is either Pre-Amendment 3 or Post-Amendment 3.

² Study part refers to pre-amendment 3 and post-amendment 3; pre-amendment 3 has both open-label and double-blind periods, post-amendment 3 has only open-label period.

³ AEs with onset more than 30 days after the last dose of study drug are excluded from analysis.

Table 5-17 Clinical Laboratory Summaries

Endpoint	Description	Timing	Methodology
Descriptives	Summary of change from baseline by laboratory	Visit F ¹ for Post-	CFB
	category and parameter in SI units and analysis	Amendment 3 and	descriptives
	visit	Visit 8 for Pre-	
	 Parameters specified in Section 6.4.2.2 	Amendment 3	
Descriptives	Summary of raw values by laboratory category	Visits A and F ¹	Continuous
	and parameter in SI units and analysis visit	for Post-	descriptives
	 Parameters specified in Section 6.4.2.2 	Amendment 3 and	
	-	Visits 1 and 8 for	
		Pre-Amendment 3	
Shift from baseline ²	Summary by laboratory category and parameter	End of Period	Shift analysis
	 Low, normal, and high categories 	within a Study	
	provided by the central laboratory	Part ²	
	• Parameters specified in Section 6.4.2.2		

¹ Pre-Amendment 3 Week 14 or End of Treatment within Pre-Amendment 3; Post-Amendment 3 Week 14 or End of Treatment within Post-Amendment 3

Laboratory assessments values meeting *any* of the PCS low or PCS high criteria specified in Section 6.4.2.1 will be identified as PCS in the laboratory data listing.

5.1.1.4.3.1 Potential Hy's Law

Potential Hy's Law criteria will be summarized by treatment group, double-blind treatment/oxybutynin chloride gel sequence, or oxybutynin chloride gel only group, as applicable, and visit for each open-label safety population as follows:

Table 5-18 Potential Hy's Law Summaries

Endpoint	Description	Timing	Methodology
Potential Hy's Law	Postbaseline assessment of the following	Study Period	Categorical
within 24-hour window	laboratory parameters based on blood draws	within Study Part ¹	descriptives
	collected within a 24-hour period:	, and the second	-
	• ALT or AST $\geq 3 \times ULN$ and		
	• TBL \geq 2 × ULN and		
	• $ALP < 2 \times ULN$		
Potential Hy's Law	Postbaseline assessment of the following	Study Period	Categorical

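### Under the current protocol, non-serious adverse events judged unrelated that start after the final visit do not reach the eCRF, so the SAP's all-cause TEAE tables are incomplete for their 30-day post-dose window

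*SAP*

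**What the plan says.** SAP 5.1.1.4.2 sets the end of the TEAE window by time alone: "An event that occurs more than 30 days after the last dose of study drug will not be considered as treatment-emergent". Table 5-15 gives the open-label upper bound as "event start date ≤ last dose date of open-label period + 30 days", and footnote 3 to Table 5-16 repeats it: "AEs with onset more than 30 days after the last dose of study drug are excluded from analysis". None of these carries a condition on seriousness or relationship. Table 5-16 then summarises TEAEs overall, by severity and by relationship, plus serious TEAEs and TEAEs leading to discontinuation, all over this one undivided window.

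Protocol 9.7.1.4 starts from a general rule: "All AEs must be recorded on the appropriate AE reporting page of the patient's eCRF whether or not they are considered causally related". A later paragraph sets a separate rule for the 30 days after the study. There, "Any AEs reported by the patient (or patient representative) during this period are to be recorded in original source documents", but "AEs are also to be recorded in the eCRF if at least one of the following conditions is met": that "the event meets the criteria for an SAE", and/or that "the event is judged by the Investigator to be potentially causally related to study treatment".

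Two further provisions fix the timing. Protocol 9.7.1 keeps events up to 30 days after the final visit (or after the last known dose, if there is no final visit) within the definition of an adverse event. Protocol 9.5.2.5 makes Visit F the end of open-label treatment and has leftover gel collected there.

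**The concern.** The analysis window and the collection rule do not match. The SAP's tail runs 30 days from the last dose, and the restricted eCRF entry starts at the final visit. For a patient who completes treatment these are nearly the same 30 days. The TEAE tables therefore join a stretch in which every event is recorded to a stretch in which one class of event is left out by design, and nothing in the table definitions tells the reader so. SAP 5.2, on changes to conduct and analysis, does not mention it either.

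At stake is what an all-cause TEAE percentage means. A reader will take it as covering treatment plus 30 days. For non-serious unrelated events it covers treatment up to the final visit only. Safety is a stated study objective, and at least 25 patients are planned after Amendment 3, so a few unrecorded events could be visible in the tables.

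**Working it through.** The documents give no figure for this point, so there is none to reproduce. The check sets the two rules side by side and then sizes the period affected.

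**Step 1. Which events are lost.** Take an event that starts after the final visit but within 30 days of the last dose.

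| Event | TEAE under SAP Table 5-15 | In eCRF under protocol 9.7.1.4 |
|---|---|---|
| Serious, related | Yes | Yes |
| Serious, unrelated | Yes | Yes |
| Non-serious, judged potentially related | Yes | Yes |
| Non-serious, judged unrelated | Yes | No, source documents only |

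Only the last class is lost. It feeds the overall TEAE row, the system organ class and preferred term rows, the severity table and the unrelated rows of the relationship table. The serious rows and the related rows do not depend on it.

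**Step 2. How long the filtered period is.** Let T be days on treatment and L the days from last dose to final visit. The TEAE window is T + 30 days. Between last dose and final visit recording is complete, so the filtered share of the window is (30 − L) / (T + 30). L is not negative, because leftover gel is collected at Visit F. The documents do not give L, so a range is shown. For a completer, T = 14 × 7 = 98:

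- L = 0: 30/128 = 23.4%
- L = 2: 28/128 = 21.9%
- L = 7: 23/128 = 18.0%
- L = 14: 16/128 = 12.5%

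A shorter treatment gives a larger share. A patient under the current protocol who stops at Week 6 (T = 42), with the termination visit on the last dosing day, has 30/72 = 41.7%. The Synopsis says in one place that only some patients receive the further 8 weeks and elsewhere describes 14 weeks for all, so the number with the shorter window is not known.

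**Step 3. From days to counts.** Day shares are not bias. SAP Table 5-2 counts a participant once per category, so a lost event changes a percentage only if that participant had no earlier event in the same row. Protocol 11.6.1 also asks for the number of events, and each lost event lowers that count by one.

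For illustration only, assume events occur at a constant rate through treatment and the tail, L = 0, T = 98, and a fraction u of all events is non-serious and unrelated. Events missing from the eCRF are then (30/128) × u of all TEAEs:

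- u = 0.3: 7.0%
- u = 0.5: 11.7%
- u = 0.7: 16.4%

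Neither the constant rate nor u comes from the documents, and these are events, not participants.

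**The case against.** The strongest case against is that little is lost and that what is lost matters least. Serious events are entered whatever their cause and related events whatever their seriousness, so the tables most used to judge the gel's safety are untouched by the filter. Participants are counted once per row, so many missed late events would change no percentage. The protocol also provides for ongoing events to be followed and for a follow-up visit within 30 days where it is thought necessary. All of this stands, and it is why the point is minor. It does not make the all-cause tables complete for the window that the SAP declares.

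Four stronger readings are tempting, and the documents do not support them.

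- A reader might infer that unequal dropout distorts the gel–placebo comparison. That comparison exists only in the Pre-Amendment 3 double-blind period, and the adverse event recording rule in force then is not in the documents; only the earlier schedule of events is reproduced, in SAP Appendix 1. Separately, Table 5-15 gives a post-dose tail only to double-blind patients who do not enter open-label treatment. That difference comes from the window definition and would remain with full recording.
- A reader might apply the same arithmetic to the 8-week Pre-Amendment 3 open-label period. It fails for the same reason: the collection rule is unknown.
- A reader might infer that related TEAE incidence is inflated. Protocol 11.6.1 takes percentages of the safety population, so leaving out unrelated events does not raise them. Only a ratio of related to all TEAEs would move, and the plan specifies none.
- A reader might see a contradiction within protocol 9.7.1.4. The sentence requiring all events is the general rule and the later paragraph is the specific one for the post-study period; the two can be read together.

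**Conclusion.** The mismatch is real for patients under the current protocol. If 9.7.1.4 is followed as written, non-serious events judged unrelated with onset after the final visit cannot enter the Table 5-16 summaries. All-cause TEAE incidence, and the incidence of non-serious unrelated TEAEs, is then incomplete for the stated window. The combined open-label tables share this gap through their Post-Amendment 3 patients.

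The size that can be shown is a period of time: on the nominal schedule, at most 30 of 128 days (23%) for a 14-week completer, falling as the gap between last dose and final visit grows. It must not be read as 23% of events or participants missing. The number affected is unknown, and the illustration above depends on assumed inputs.

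The conclusion assumes that sites apply the post-study paragraph, rather than the general rule, after the final visit. It makes no claim about the double-blind comparison or about Pre-Amendment 3 data. Severity: minor.

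**What to change.** Either of two changes would do.

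1. **Align collection with analysis.** Amend protocol 9.7.1.4 so that every adverse event reported in the 30-day post-study period is entered in the eCRF. Reported events are already in source documents, so for patients who have finished, enter them retrospectively where possible. That keeps one capture rule across the Post-Amendment 3 tables. Cost: one protocol sentence and some data entry.

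2. **Leave collection as it is and make the limit visible.** Keep the tables that run to last dose + 30 days, so that late related events stay in the main summaries, and footnote them to say that non-serious events judged unrelated were not collected in the eCRF after the final visit. Add a TEAE summary ending at the final protocol-defined visit, where capture is complete, and tabulate later serious or related events separately. Cost: a short SAP addition and one extra set of tables.

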5.1.1.4.3 Clinical Laboratory Assessments

Clinical laboratory assessments will be summarized by treatment group, double-blind treatment/oxybutynin chloride gel sequence, or oxybutynin chloride gel only group, as applicable, and by analyte and visit for each safety population. Study Part is either Pre-Amendment 3 or Post-Amendment 3.

² Study part refers to pre-amendment 3 and post-amendment 3; pre-amendment 3 has both open-label and double-blind periods, post-amendment 3 has only open-label period.

³ AEs with onset more than 30 days after the last dose of study drug are excluded from analysis.

Table 5-17 Clinical Laboratory Summaries

Endpoint	Description	Timing	Methodology
Descriptives	Summary of change from baseline by laboratory	Visit F ¹ for Post-	CFB
	category and parameter in SI units and analysis	Amendment 3 and	descriptives
	visit	Visit 8 for Pre-	
	 Parameters specified in Section 6.4.2.2 	Amendment 3	
Descriptives	Summary of raw values by laboratory category	Visits A and F ¹	Continuous
	and parameter in SI units and analysis visit	for Post-	descriptives
	 Parameters specified in Section 6.4.2.2 	Amendment 3 and	
	-	Visits 1 and 8 for	
		Pre-Amendment 3	
Shift from baseline ²	Summary by laboratory category and parameter	End of Period	Shift analysis
	 Low, normal, and high categories 	within a Study	
	provided by the central laboratory	Part ²	
	• Parameters specified in Section 6.4.2.2		

¹ Pre-Amendment 3 Week 14 or End of Treatment within Pre-Amendment 3; Post-Amendment 3 Week 14 or End of Treatment within Post-Amendment 3

Laboratory assessments values meeting *any* of the PCS low or PCS high criteria specified in Section 6.4.2.1 will be identified as PCS in the laboratory data listing.

5.1.1.4.3.1 Potential Hy's Law

Potential Hy's Law criteria will be summarized by treatment group, double-blind treatment/oxybutynin chloride gel sequence, or oxybutynin chloride gel only group, as applicable, and visit for each open-label safety population as follows:

Table 5-18 Potential Hy's Law Summaries

Endpoint	Description	Timing	Methodology
Potential Hy's Law	Postbaseline assessment of the following	Study Period	Categorical
within 24-hour window	laboratory parameters based on blood draws	within Study Part ¹	descriptives
	collected within a 24-hour period:	, and the second	-
	• ALT or AST $\geq 3 \times ULN$ and		
	• TBL \geq 2 × ULN and		
	• $ALP < 2 \times ULN$		
Potential Hy's Law	Postbaseline assessment of the following	Study Period	Categorical
without window	laboratory parameters at any time:	within Study Part ¹	descriptives
(e-DISH)	• Maximum ALT or AST $\geq 3 \times ULN$		
	• Maximum TBL $\geq 2 \times ULN$		

e-DISH = evaluation of drug-induced serious hepatotoxicity.

ALT = alanine aminotransferase; AST = aspartate aminotransferase; TBL = total bilirubin.

ALP = alkaline phosphatase; ULN = upper limit of normal.

Study part refers to pre-amendment 3 and post-amendment 3; pre-amendment 3 has both open-label and doubleblind periods, post-amendment 3 has only open-label period.

² Study part refers to pre-amendment 3 and post-amendment 3; pre-amendment 3 has both open-label and double-blind periods, post-amendment 3 has only open-label period.

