9 INVESTIGATIONAL PLAN

9.1 Overall Study Design and Plan

This *study was initiated as* a double-blind, placebo-controlled study *with an open-label extension, and is now amended to continuing to enroll patients under only open-label treatment*.

Pre-Amendment 3, patients ages 6 to >17 years, were randomly assigned 1:1 to receive doubleblind oxybutynin chloride gel or placebo gel for 6 weeks, followed by an open-label, 8-week period to generate safety data. All patients began treatment with 0.75 g of gel/day for 2 weeks. Patients then returned to the clinic for a potential dose titration and at this time their dose could have been adjusted up to 1 g/day, down to 0.5 g/day, or remained the same at 0.75 g/day. The determination of dose was based on the investigator's clinical judgment and assessment of the patient's bladder symptoms and treatment side effects.

Dose titration was permitted only once during the entire 6-week double-blind, placebocontrolled period. Patients continued blinded treatment for 4 additional weeks until the end of the double-blind treatment period. Pre-Amendment 3, visits were identified numerically (ie, Visit 1 through Visit 8/Early Termination).

Post-Amendment 3, this study will continue as an open-label study for new patients enrolled under the present protocol (Amendment 3), with a similar patient population (ie, pediatric patients who have been diagnosed with detrusor overactivity that is associated with a neurogenic condition) and will also enroll younger patients (minimum age of 3 years).

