9.7.1.7 Potential Hy's Law Cases

Criteria for potential Hy's Law cases are as follows:

- Alanine Aminotransferase or Aspartate Aminotransferase ≥ 3x upper limit of the normal range (ULN) AND
- Total Bilirubin $\geq 2xULNAND$
- Alkaline Phosphatase < 2xULN

Study site personnel must report every patient who meets these potential criteria. Typically, all 3 analytes will be obtained from the same sample, but they may come from multiple samples taken within a 24-hour period. This requirement applies from the time he or she signs the ICF for the trial until 30 days after the final protocol-defined study visit or the last known dose of study treatment (if the final visit does not occur).

A laboratory alert for potential Hy's laws cases will be in place and must notify investigators and the Sponsor immediately when the above criteria have been met. A potential Hy's law case must be faxed to the Sponsor on an AE of Special Interest Form as soon as possible (within 24 hours of learning of the potential Hy's law) to the SAE/Pregnancy fax number stated in Section 9.7.1.5, even if no AE has occurred. The eCRF for potential Hy's law cases must be completed within 7 calendar days. Every effort to determine the cause of the liver enzyme abnormalities must be made, and close monitoring should be initiated in conjunction with the medical monitor and in accordance with the FDA "Guidance for Industry: Drug Induced Liver Injury-Pre-Marketing Clinical Evaluation" July 2009.

Medical Emergencies and Emergency Protocol Deviations

In medical emergencies, the investigator will use medical judgment and remove the patient from immediate harm. The investigator will then immediately notify the sponsor and the IRB regarding the type of emergency and the course of action taken.

An investigator shall notify the *sponsor's medical safety physician* and the reviewing IRB of any deviation from the investigational plan to protect the life or physical well-being of a patient in an emergency. Such notice shall be given as soon as possible, but in no event later than 5 working days after the emergency occurred. Except in such an emergency, prior approval by the sponsor is required for any changes in or deviations from the protocol. All deviations must be documented on the *eCRF*.

The following contact will be used for all communications with the medical safety physician of this study:

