5.1.1.1 Common Conventions

5.1.1.1.1 Analysis Populations

The analysis populations will consist of participants as defined below, where analysis populations are formed relative to the protocol under which a participant was enrolled. Participants enrolled prior to protocol amendment 3 are referred to as "pre-amendment 3," and participants enrolled under protocol amendment 3 or later are referred to as "post-amendment 3." For example, the pre-amendment 3 safety population consists of all treated participants who received blinded study treatment and may have also received open-label active treatment. The post-amendment 3 safety population consists of all treated participants who received open-label active treatment. Details are below with categorizations based on double-blind or open-label treatment.

[figure not shown]

Table 5-1 Analysis Populations

Population	Definition	Study Treatment
Post-Amendment 3 open- label Safety	All participants who receive at least 1 dose of study treatment in the open-label period who are enrolled under Amendment 3 or	Actual received ¹
Pre-Amendment 3 double-blind Safety	All participants who receive at least 1 dose of study treatment in the double-blind period, which is only applicable to participants who enrolled prior to Amendment 3	Actual received ¹
Pre-Amendment 3 open- label Safety	All participants who receive at least 1 dose of study treatment in the open-label period before Amendment 3	Actual received ¹
Combined open-label Safety (Pre- and Post- Amendment 3)	All participants who receive at least 1 dose of study treatment in the open-label period before or after Amendment 3	Actual received ¹
Post-Amendment 3 Intent-to-Treat (ITT) ²	All participants who receive at least 1 dose of study treatment and have at least one post-baseline value for the primary efficacy variable in the Post-Amendment 3 open-label period	Actual received ¹
Pre-Amendment 3 (Intent-to-Treat) ITT ²	All randomized participants who have at least one post-baseline value for the primary efficacy variable in the Pre-Amendment 3 double-blind period	Randomized assignment

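### The SAP's Hy's Law and e-DISH summaries name only the open-label safety populations, so Pre-Amendment 3 patients who stopped before any open-label dose are left out, contrary to the SAP's own general safety rule

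*SAP*

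**What the plan says.** **Hy's Law text.** SAP 5.1.1.4.3.1 introduces Table 5-18 with groupings that are to apply "as applicable, and visit for each open-label safety population as follows". The table has two rows: the three-part criterion within a 24-hour window, and the e-DISH criterion (maximum ALT or AST with maximum total bilirubin, at any time).

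**Populations (SAP Table 5-1).**
- Pre-Amendment 3 open-label safety: "All participants who receive at least 1 dose of study treatment in the open-label period before Amendment 3".
- Combined open-label safety: "All participants who receive at least 1 dose of study treatment in the open-label period before or after Amendment 3".
- Pre-Amendment 3 double-blind safety: "All participants who receive at least 1 dose of study treatment in the double-blind period".

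**Neighbouring rules.** SAP 5.1.1.4 bases safety analyses on every safety population. The parent laboratory section, 5.1.1.4.3, does the same: "as applicable, and by analyte and visit for each safety population". The timing column of Table 5-18 is each study period within each part of the study, and the footnote explains that "pre-amendment 3 has both open-label and doubleblind periods".

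**Laboratory schedule.** Protocol 9.7.2 gives Pre-Amendment 3 chemistry at Visit 1 and Visit 8. The schedule in SAP Appendix 1 marks it at Visit 1 and in the column headed Visit 8/ET. Protocol 9.1 describes the Pre-Amendment 3 visits as "Visit 1 through Visit 8/Early Termination".

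**The concern.** The population named in the Hy's Law sentence is narrower than the one that governs every other laboratory summary, and nothing in the SAP explains why. The list of analysis changes in SAP 5.2.2 records no decision to narrow it.

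The patients removed are those who took double-blind gel or placebo and never took an open-label dose. They can have a post-baseline liver sample, because early termination shares a schedule column with Visit 8. A programmer who follows the sentence would build both rows of Table 5-18 without them. At stake is whether the liver-safety count is complete: one potential case matters, and a count of zero can be read as zero only if everyone with a post-baseline sample is in the denominator.

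**Working it through.** The SAP gives no figure for this point. It is settled by setting the definitions side by side; the arithmetic only indicates scale.

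**Step 1: who is in the named populations.**

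| Patient | Double-blind safety | An open-label safety population | In the Hy's Law summaries as written |
|---|---|---|---|
| Pre-Amendment 3, entered open-label | yes | yes | yes |
| Pre-Amendment 3, dosed double-blind, no open-label dose | yes | no | **no** |
| Post-Amendment 3, dosed | not applicable | yes | yes |

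Only the middle row is affected. The SAP expects such patients: Table 5-15 has a separate treatment-emergent rule for those who do not enter the 8-week open-label period, and the Week 6 window in Table 6-4 has a branch for them.

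**Step 2: whether they can have data.** No chemistry is scheduled between Visit 1 and Visit 8/ET. The only scheduled post-baseline chemistry that can fall in the double-blind period is therefore a termination sample from a patient in the middle row.

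**Step 3: whether the timing column repairs the population.** It does not. Timing selects results from patients already admitted. For patients who went on to open-label gel, the double-blind period holds no scheduled chemistry (Step 2). Read literally, the double-blind part of Table 5-18 could contain only unscheduled samples.

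**Step 4: scale.** Inputs, from SAP 5.1.2: 48 per arm, 96 in total, 10% dropout, difference 20, SD 28.
- Check on the planning figures, with two-sided alpha 0.05 assumed because that section states none. Normal approximation: power = Φ(20 / (28 × √(2/n)) − 1.96).
  - n = 48: Φ(3.499 − 1.96) = 0.938, or 0.934 by noncentral t; the plan says 93%.
  - n = 43 (48 × 0.90 = 43.2): Φ(3.312 − 1.96) = 0.912, or 0.906 by noncentral t; the plan says 90%.
  - The 10% is therefore consistent with a loss of about 5 per arm.
- Patients lost: 48 × 0.10 = 4.8 per arm; 96 × 0.10 = 9.6 in total.
- Other assumed rates: 5% gives 96 × 0.05 = 4.8 in total; 20% gives 96 × 0.20 = 19.2.

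These are ceilings for each rate. They take planned enrolment as achieved, put all dropout before open-label entry and assume every leaver was sampled.

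**The case against.** **It may be a drafting slip.** The general rule, the parent section and the footnote all point to the double-blind period being meant, and the sentence itself lists treatment group among its groupings. That is plausible and makes the correction easy. It does not remove the need for it, since the sentence is the specific instruction for these summaries.

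**Termination samples are not certain.** Visit 8/ET sits under the open-label heading in both the Pre-Amendment 3 schedule and Table 6-4. The detailed termination instructions in Protocol 9.5.3 and 9.5.4 belong to the Post-Amendment 3 procedures, and 9.5.3 asks for exit assessments only where possible. This stands: the samples are scheduled, but their existence is not established.

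**The patients are not lost from all reporting.** This also stands. They may appear in the double-blind laboratory summaries and shift tables. ALT or AST of at least 3 times ULN, and bilirubin above 1.5 times ULN, are flagged in the listing under SAP 6.4.2.1. Clinically significant out-of-range changes become adverse events under Protocol 9.7.2, and cases meeting the criteria are reported within 24 hours. None of these routes is a tabulated count of the combined criterion.

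Three stronger readings are tempting and are not supported:
- *A placebo comparison of liver safety is lost.* No Week 6 chemistry is scheduled, and everyone who reaches Week 14 has switched to gel. There is no scheduled placebo comparison to lose, only a few self-selected leavers per arm.
- *The SAP contradicts the protocol's case-reporting rule.* Protocol 9.7.1.7 says "This requirement applies from the time he or she signs the ICF for the trial", but that is a reporting duty on sites and does not define an analysis population. Protocol 11.6.3 asks for no Hy's Law table.
- *The omitted patients stopped for safety reasons.* The documents give no reasons for stopping.

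**Conclusion.** The point holds as an internal conflict in the SAP with a practical consequence. If 5.1.1.4.3.1 is followed as written, Pre-Amendment 3 patients with no open-label dose are missing from the Hy's Law and e-DISH summaries, while the general safety rule would include them. Post-Amendment 3 patients are unaffected.

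The size is small and uncertain. Under the planned 10% dropout it is at most about 5 per arm, and 0 to 10 in total is a plausible range. That rests on the planned enrolment and dropout rate, on all dropout falling before open-label entry, and on every leaver being sampled; the documents confirm none of these. The correction is worth making because it completes a liver-safety count at almost no cost. It would not change any efficacy conclusion or create a comparative safety analysis.

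**What to change.** 1. In SAP 5.1.1.4.3.1, make the summaries apply *for each safety population*, in line with 5.1.1.4 and the parent laboratory section. Show the Pre-Amendment 3 double-blind safety population by treatment group, labelled descriptive.
2. State in SAP 6.2.2 that a termination sample taken before open-label entry belongs to the double-blind period. Table 6-4 lists Visit 8/ET only under open-label, with a window counted from the first open-label dose, so such a sample now has a visit label in one period and a treatment day in the other.
3. Report how many patients in each group have a post-baseline liver sample, so that the denominators are visible.

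The cost is a change of phrase, one windowing rule and one more set of columns. The e-DISH row needs only ALT, AST and total bilirubin, all of which are in the protocol's chemistry panel. The 24-hour row also needs alkaline phosphatase, which Protocol Appendix 2 does not list although SAP Table 6-10 does. Its availability for these samples should be confirmed before that row is promised.
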